¹⁵ MRI assessments should be completed within 5 days prior to the scheduled dose administration, with the exception of the Day 1 MRI which may be completed within 14 days prior to Day 1 visit. MRI assessments during the follow-up period (Day 358/ET and Day 393/EOS) have a ± 5 day window.

¹⁶ 10-meter walk/run, 6-minute walk, 100-meter timed test (Part 2, open-label only; starting at the Dose 10 visit and continuing through to the EOS visit at all timepoints noted). Tests may be performed within 3 days prior to Day 1 visit.

¹⁷ Gait parameters, Berg balance scale. Tests may be performed within 3 days prior to Day 1 visit.

¹⁸ Maximum voluntary isometric contraction testing will be conducted using a handheld dynamometer. Both sides will be tested (right and left).

¹⁹ CMTES2 to be assessed by investigator; CMT-HI to be completed by patient

²⁰ Randomization should occur within 24 hours prior to Day 1 dose.

²¹ PamSysTM device is a physical activity monitoring system that will be worn by the patient for the duration of the study.

²² Study drug administration should occur within 21 days (\pm 3 days) of the previous dose.

²³ If subjects enroll directly into a separate extension study and will receive additional treatment with ACE-083, they do not need to complete the EOS visit. For these subjects, their final Study Visit in this protocol will be the ET visit.

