#### **Part 2**

- To evaluate changes in biomarkers
- To evaluate changes in tibialis anterior (TA) compound muscle action potential (CMAP)
- To evaluate changes in gait, activity level, and fall parameters
- To evaluate changes in motor function via the 100-meter timed test

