## 4. STATISTICAL METHODS

### 4.1. General Method

#### 4.1.1. Sample Size Determination

There was no formal sample size calculation for Part 1. Six patients in each cohort will provide sufficient data to evaluate safety and a preliminary assessment of changes in muscle volume and muscle strength.

The sample size calculation for Part 2 is based upon the percent change from baseline in total muscle volume of the injected TA muscle 3 weeks after the last dose. A 10% difference between ACE-083-treated and placebo groups in the percent change in total muscle volume from baseline is considered to be clinically meaningful. The standard deviation (SD) is assumed to be approximately 10% for each group, based on preliminary MRI data for the ACE-083-treated side from the initial TA cohort in Part 1 of the Phase 2 study in FSHD patients.

Assuming a 2-sided type I error rate of 0.10, a 10% difference in percent change from baseline between ACE-083-treated and placebo groups in total muscle volume, a standard deviation of 10% for each group, and a 1:1 randomization, 90% power is achieved with a total sample size of 36 (18 active, 18 placebo), based on a standard t-test.

In addition, this sample size also provides 90% power to detect a 10% difference in 6-minute walk test distance, based on a similar estimated SD of 10% (based off of available data from Part 1 of the Phase 2 study in FSHD patients as well as data from Part 1 of this study, 3-weeks post last dose) and a 2-sided type 1 error rate of 0.10.

In order to account for dropouts (up to 10%), 40 patients will be randomized to study treatment for each muscle (20 active, 20 placebo) to ensure that at least 18 patients per treatment group complete the double-blind treatment period.

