### **Falls**

The hazard ratio of recurring falls between ACE-083 and placebo during the entire 12 months (excluding the screening interval) will be estimated using the Andersen-Gill recurrent events model with the following covariates: SEQUENCE, CMT-TYPE, PERIOD, and ankle dorsiflexion MRC-MMT decimal score where SEQUENCE refers to the treatment sequence from double-blind to open-label (ACE-083  $\rightarrow$  ACE-083 or Placebo  $\rightarrow$  ACE-083), and PERIOD

refers to the period of time of observation (“Double-blind”, “Open-label”). The “Double-Blind” period covers Weeks 1 to 24 and the “Open-label” period covers Weeks 25 to 48. The point estimate, p-value and 90% confidence interval for the hazard ratio for SEQUENCE will be provided.

Additional methods for the statistical analysis of the recurring event of falls may be considered and performed as appropriate (e.g. negative binomial regression with similar covariates as listed for the Andersen-Gill recurrent events model described above).

No multiple imputations will be performed for missing data.

The statistical analyses described above will be done on the Per Protocol Set and will be considered primary. The analyses described above will also be repeated for the Full Analysis Set.

Additional analyses may be performed as appropriate.

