## **4.9. Subgroup Analyses**

Subgroup analyses will be performed for selected efficacy and pharmacodynamics data from the double-blind period of Part 2.

Subgroups consist of the following:

- Ankle Dorsiflexion MRC-MMT Grade {weaker of two sides at Screening}: (3 to 4-; 4 to 4+)
- Ankle Dorsiflexion Screening MRC-MMT Grade of 4- to 4+ on both left and right sides
- Plantar Flexion MRC-MMT Grade {weaker of two sides at Screening}: (4- to 4+; 5- to 5)
- Knee Extension MRC-MMT Grade {weaker of two sides at Screening}: (3+ to 4+; 5- to 5)
- MRC-MMT Grade {weaker of two sides at Screening} for plantar flexion and knee extension
  - Levels are “Both 5- to 5” and “Not both 5- to 5”.
  - “Both 5- to 5” means that the MRC-MMT grade {weaker of two sides} for both plantar flexion and knee extension must both be between 5- and 5.

- “Not both 5- to 5+” means that the MRC-MMT grade {weaker of two sides} for any or both plantar flexion and knee extension should not both be between 5- and 5+. For example, a patient with plantar flexion MRC-MMT grade {weaker of two sides} of a 5- and knee extension MRC-MMT grade {weaker of two sides} of 4 would be classified as “Not both 5- to 5+”.
- Baseline Fat Fraction (%): (< median;  $\geq$  median)
- CMT type: (CMT1, CMTX)
- CMT gene mutation: (CMT1A, not CMT1A)
- Usage of Braces (Yes; No)
  - This information is contained in the individual patient’s CMT disease history
- Dose per Calculated Contractile Muscle Mass (mg/g): (< median;  $\geq$  median)
- Exercise Program: (resistance; no resistance)
  - The “resistance” subgroup includes patients who responded “Yes” to the question “Does the patient have a regular (at least once a week) exercise program?” and reported “Resistance training” as a type of exercise program.
  - The “no resistance” subgroup includes patients who responded “Yes” to the question “Does the patient have a regular (at least once a week) exercise program?” and did not report “Resistance training” as a type of exercise program.
- Baseline CMT-HI Total Score: (< median;  $\geq$  median)
- Activity level (steps/d): (< median;  $\geq$  median)
  - This is defined as the average number of steps per day as measured by the PAMSys™ device over the patient’s study participation in the Part 2 double-blind period, adjusted for overall compliance in using the device to record such activity.
- ADA (ADA +; ADA-)

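### The SAP 4.9 activity-level subgroup is formed from steps recorded during double-blind treatment, so the comparisons within its two halves are not protected by randomisation and can be biased.

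*SAP*

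**What the plan says.** SAP 4.9 lists activity level (steps per day, below versus at or above the median) among the Part 2 subgroups. Steps are averaged over the patient's "study participation in the Part 2 double-blind period, adjusted for overall compliance in using the device to record such activity". For each subgroup category the section then estimates the treatment effect with an ANCOVA and tests it at two-sided 0.10 with a 90% confidence interval, for 15 listed parameters. These include 6-minute walk distance (6MWD), the 10-meter walk/run, several CMT-HI scores and falls.

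The same quantity is an outcome elsewhere. SAP 2.3 gives as a Part 2 exploratory objective "To evaluate changes in gait, activity level, and fall parameters", and SAP 4.7.1.2 defines activity level among the motor function variables.

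The device is handed out before treatment. Protocol Appendix 1, Table 6, places its distribution at Screening (Day -28 to Day -7), and footnote 21 says the "device is a physical activity monitoring system that will be worn by the patient for the duration of the study". The 12-month falls model in SAP 4.7.2.2.3 leaves out a screening interval.

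SAP 4.9 calls its subgroup findings hypothesis generating and does not control the overall type I error.

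**The concern.** A subgroup comparison inherits the protection of randomisation only if membership is settled before treatment can influence it. Here membership depends on up to six months of on-treatment behaviour. If ACE-083 raises steps, some treated patients cross into the upper half who would have been in the lower half on placebo. The treated patients in the upper half are then, on average, of lower underlying activity than the placebo patients beside them, and the same holds in the lower half. If underlying activity is related to the endpoint, both within-half differences shift in the same direction.

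What is at stake is the use of these results for planning. A later trial can select or stratify on activity before treatment, but not on steps taken during treatment. The comparable median splits in SAP 4.9, on fat fraction and CMT-HI total score, use baseline values.

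**Working it through.** **The plan's own figure.** SAP 4.1.1 assumes "a standard deviation of 10% for each group, and a 1:1 randomization", a 10-point difference and two-sided alpha 0.10, and states that "90% power is achieved with a total sample size of 36 (18 active, 18 placebo), based on a standard t-test". The normal formula gives 2 × (1.645 + 1.282)² × (10/10)² = 17.1, so 18 per arm. Noncentral t power at 18 per arm is 90.2%, and 36/0.90 = 40 randomised. The figure reproduces. The SAP applies the same difference and SD to 6MWD. It states no figure for the activity subgroup.

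**Precision within a half.** With 36 evaluable patients and an even split there are 9 per arm in each half.
- SE = 10 × √(2/9) = 4.71.
- The 90% half-width with 16 degrees of freedom is 1.746 × 4.71 = 8.2 points.
- Power for a 10-point effect is about 65%.

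**Bias formula.** Let z be underlying activity in SD units, d the drug effect on steps in SD units, and ρ the correlation of z with the endpoint residual (SD 10). With 1:1 allocation the pooled median lies at d/2. A treated patient is in the upper half if z > -d/2, a placebo patient if z > d/2. The difference in mean z in the upper half is φ(d/2)/Φ(d/2) - φ(d/2)/[1 - Φ(d/2)], and by symmetry it is the same in the lower half. The bias is that difference × ρ × 10.

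Both d and ρ are assumptions; the documents give neither.
- d = 0.5: 0.387/0.599 - 0.387/0.401 = -0.318 (with unrounded inputs). Bias is -0.318 × 0.3 × 10 = -1.0 at ρ = 0.3 and -0.318 × 0.5 × 10 = -1.6 at ρ = 0.5. About 60% of the upper half is on ACE-083.
- d = 1: the difference in mean z is -0.632. Bias at ρ = 0.5 is -0.632 × 0.5 × 10 = -3.2. About 69% of the upper half is on ACE-083.
- d = 0 or ρ = 0: bias is zero. Negative ρ reverses the sign.

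A simulation of 1,000,000 patients per setting agrees:

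| d | ρ | Bias, lower half | Bias, upper half |
|---|---|---|---|
| 0.25 | 0.5 | -0.79 | -0.76 |
| 0.5 | 0.3 | -0.95 | -0.97 |
| 0.5 | 0.5 | -1.55 | -1.58 |
| 1 | 0.5 | -3.17 | -3.17 |

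These rows use a true effect of 10. With a true effect of 0 the biases are the same apart from simulation noise. Against the planned 10 points, a bias of -1.0 to -1.6 is 10 to 16%, and -3.2 is 32%.

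**Type I error within a half** (nominal 0.10; 5,000 trials of 18 per arm, t-test; Monte Carlo SE √(0.1 × 0.9/5,000) = 0.004):
- d = 0.5, ρ = 0.3: 0.112 (lower half) and 0.105 (upper half).
- d = 0.5, ρ = 0.5: 0.119 and 0.131.
- d = 1, ρ = 0.5: 0.158 and 0.160.
- d = 0, ρ = 0.5: 0.098 and 0.104.

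**After the fix.** Splitting on a pre-dose step count, assumed to correlate 0.8 with on-study steps, gives a bias within 0.04 points, a 50/50 split of each arm, and type I error of 0.095 and 0.099.

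**The case against.** The case for leaving the plan alone has real weight. SAP 4.9 offers these results only as leads for future study, and this is one of more than a dozen subgroups. The primary muscle volume analysis and the whole-population 6MWD and falls analyses do not use the split. In the 0.5 SD illustrations a bias of 1.0 to 1.6 points sits inside a half-width of 8.2. Protocol exclusion criterion 15 keeps out patients who cannot hold their activity at the baseline level, which may limit any change in steps and makes a 1 SD rise less plausible. The planned models adjust for baseline and, for 6MWD, height; the illustration does not, so the relevant residual correlation could be lower than assumed. All of this stands, and it sets the priority. It does not restore randomisation within the halves: the hypothesis-generating label deals with multiplicity, not with how membership is formed, and criterion 15 does not fix step counts.

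A reader might go further and infer that both estimates are biased and that the drug effect is understated throughout. The documents do not support that. Bias needs both a drug effect on steps and a steps-endpoint correlation, and its direction follows the sign of the correlation. For falls the direction is especially unclear: more walking may mean more exposure to falling, and a fall may reduce walking. Nor do the documents say that ACE-083 is intended to raise steps. The objective is exploratory and speaks of evaluating changes, Protocol 5.2 describes improved mobility only as a possibility, and SAP 4.7.2.2.1 plans a listing with optional exploratory analyses of activity level.

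A reader might also take a pre-treatment step count as already available. Distribution at Screening makes it likely, but neither document defines such a measure or a minimum wear time.

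**Conclusion.** The point holds as a minor one. Subgroup membership is post-randomisation, the variable is one that the SAP also evaluates as an outcome, and no other section corrects the definition. The within-half comparisons can therefore be biased, by an amount the documents do not allow anyone to fix. Under the assumptions above the size runs from zero to about 1.0 to 1.6 points at a 0.5 SD rise in steps, and to about 3.2 points at 1 SD with correlation 0.5. The bias in points does not depend on the true effect, so the percentages apply to the planned 10-point 6MWD difference; for a true effect half that size they would double. Only 6MWD-type outcomes with SD 10 were worked through, so neither size nor direction should be carried over to falls, the 10-meter walk/run or CMT-HI. The primary and whole-population conclusions are not affected.

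**What to change.** In SAP 4.9, define the activity subgroup by mean steps per day from device distribution at Screening to the day before the first dose, cut at the pooled median, with the same wear-time adjustment. Device distribution between Day -28 and Day -7 leaves roughly one to four weeks of possible wear. If pre-dose wear proves too sparse, drop the subgroup, or report it only as a descriptive, non-randomised summary without within-half tests.

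The cost is one SAP sentence, best changed before unblinding. The downside is fewer wear days per patient and the loss of a few patients with no pre-dose wear. The ADA subgroup in the same section is also formed from double-blind data; this change does not address it.

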  - ADA+ means that the patient had positive ADA for ACE-083 at least once during the double-blind period of Part 2
  - ADA- means that the patient did not have positive ADA for ACE-083 at least once during the double-blind period of Part 2

Subgroup analyses will be performed for the following parameters:

- Day 190 average percent change in total muscle volume from baseline
- Day 190 average percent change in calculated contractile muscle volume from baseline
- Day 190 average absolute change in fat fraction from baseline
- Day 190 average percent change in fat fraction from baseline
- Day 190 average percent change in ankle dorsiflexion MVIC from baseline

- Day 190 average absolute change in ankle dorsiflexion MMT-MRC decimal score from baseline
- Day 190 percent change in 6MWD from baseline
- Day 190 percent change in time to complete 10mW/R from baseline
- Day 190 absolute change in CMT-HI total score from baseline
- Day 190 absolute change in CMT-HI foot/ankle strength subscale score from baseline
- Day 190 absolute change in CMT-HI balance subscale score from baseline
- Day 190 absolute change in CMT-HI fatigue subscale score from baseline
- Day 190 absolute change in CMT-HI mobility subscale score from baseline
- Day 190 absolute change in CMT-HI activities subscale score from baseline
- Fall risk reduction during double-blind period

Subgroup analyses will be performed using similar ANCOVA models described in previous sections for each subgroup category provided that the sample size is at least 4. Because of the reduced sample size within each subgroup category, it is not planned to include CMT-TYPE into such models. For each subgroup category, the treatment effect will be estimated and tested using a 0.1 (two-sided) significance level with the corresponding 90% confidence interval. Bar charts of the least squares mean estimates ( $\pm$  SEM) for each of the treatment groups will be provided.

For purposes of this study, findings of subgroup analyses are considered to yield hypothesis generating statements for future study. It is not planned to control the overall type-1 error.

Additional analyses may be performed as appropriate.

Data from multiple imputations described in [Section 4.7.2.2.1](#) will be used.

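### The subgroup plan tests the treatment effect within each level at 0.10 but never estimates the difference between levels, so nothing planned measures effect modification

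*SAP*

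**What the plan says.** SAP 4.9 lists 13 two-level subgroup factors and one single-level subgroup (screening dorsiflexion grade 4- to 4+ on both sides), and 15 parameters. A model like the main ANCOVA is fitted in each level that has at least 4 patients, without CMT-TYPE. Then: "For each subgroup category, the treatment effect will be estimated and tested using a 0.1 (two-sided) significance level with the corresponding 90% confidence interval". The adjusted means per arm are also to be plotted.

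On status, the SAP says that "findings of subgroup analyses are considered to yield hypothesis generating statements for future study", and it declines to control the overall type I error.

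The only interaction terms named anywhere in the SAP are baseline by cohort (Part 1) and treatment by visit (the repeated-measures sensitivity models). Protocol 14.2.3 and 14.2.4 likewise ask only for an estimate and 90% CI within the 4- to 4+ dorsiflexion group.

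**The concern.** Nearly all the subgroups come as pairs: CMT1 and CMTX, below and above the median, braces or none. A paired layout invites the question whether the effect differs between the two levels. The plan answers a different question twice, namely whether the effect in each level differs from zero. With about half the sample in each level, power within a level is moderate, and one level can easily pass 0.10 while the other does not, although the true effects are the same.

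What is at stake is the quality of the hypotheses that the section exists to generate. A hypothesis about who responds better concerns the between-level difference, and no planned statistic estimates it with its uncertainty. The general allowance for additional analyses does not pre-specify one.

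**Working it through.** **Inputs (SAP 4.1.1).**

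- Error rate: "Assuming a 2-sided type I error rate of 0.10".
- Effect to be detected: "a 10% difference in percent change from baseline between ACE-083-treated and placebo groups in total muscle volume".
- Spread and allocation: "a standard deviation of 10% for each group, and a 1:1 randomization".

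The plan states that "90% power is achieved with a total sample size of 36 (18 active, 18 placebo), based on a standard t-test", and "In order to account for dropouts (up to 10%), 40 patients will be randomized to study treatment". The same difference and SD are assumed for 6-minute walk distance: "this sample size also provides 90% power to detect a 10% difference in 6-minute walk test distance".

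**Reproducing the plan's figure.** For a two-sample t-test with n per arm, the noncentrality is 10 / (10 × √(2/n)) on 2n − 2 df. At n = 18 it is 3.00 on 34 df and power is 90.2% (88.7% at n = 17). Allowing for 10% dropout, 36 / 0.9 = 40. The stated figures reproduce.

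**Same effect in two equal halves.** Assume the arms are balanced within each half. The halves contain different patients, so the two tests are independent and, with power p in each, the chance that exactly one is significant is 2p(1 − p).

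- 9 per arm per half (36 patients): noncentrality 2.12, 16 df, p = 0.650. Exactly one: 2 × 0.650 × 0.350 = 45.5%. Both 42.3%, neither 12.2%.
- 10 per arm per half (40 patients): noncentrality 2.24, 18 df, p = 0.694. Exactly one: 2 × 0.694 × 0.306 = 42.5%.

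Removing one df for a baseline covariate gives 45.6% and 42.6%. In 200,000 simulated trials at 9 per arm per half, discordance was 45.4%; a 0.10-level interaction test on the same data rejected in 10.0%.

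**Sensitivity to the common true effect (SD 10).**

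| True effect in both halves | 9 per arm | 10 per arm |
|---|---|---|
| 0 | 18.0% | 18.0% |
| 5 | 39.3% | 41.0% |
| 7.5 | 49.5% | 50.0% |
| 10 | 45.5% | 42.5% |
| 12.5 | 30.3% | 25.3% |
| 15 | 14.9% | 10.8% |

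At an effect of 10 and 9 per arm, SD 8, 12 and 15 give 30%, 50% and 47%. Unequal levels do worse at the design effect: assumed per-arm sizes of 14 and 6 give 51%, 16 and 4 give 61%, 18 and 2 give 76%.

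**Precision of the missing estimate.** With four cells of n patients, the SE of the interaction is 10 × √(4/n).

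- n = 9: SE 6.7; 90% CI half-width 1.694 × 6.67 = 11.3 points (32 df); power 43% for a true 10-point difference between halves; 80% power needs about 17 points.
- n = 10: SE 6.3; half-width 10.7 points; power 46%; 80% power needs about 16 points.

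**The case against.** The best defence is that SAP 4.9 prescribes no comparison of significant with non-significant levels. It gives an estimate and a 90% CI in each level, and from two disjoint groups a reader can form the difference and an approximate CI by hand. The analyses are openly exploratory, in a 40-patient phase 2 trial. This stands in part: the 42.5% to 45.5% measures a misreading that the layout invites, not a rule in the plan. It does not remove the gap, because the between-level estimate is still left to the reader. The exploratory label and the waiver of error control deal with multiplicity, which is a different matter.

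A second defence is that the interaction has low power, so setting 10% false flags against about 45% discordance shows only one side. That is fair, and the 43% power belongs beside those figures. It argues for reporting an interval rather than relying on a p-value.

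Third, a blanket interaction model would fail for some listed factors, and this stands in full:

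- ADA status and activity level are measured during double-blind treatment, so they are not baseline modifiers.
- Dose per contractile muscle mass is derived from the ACE-083 dose injected (SAP 4.4.2), which placebo patients do not have.
- Both exercise levels require a regular programme, so patients without one belong to neither.
- The single-level 4- to 4+ dorsiflexion subgroup has no comparator, and the protocol asks only for the effect within it.

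**Conclusion.** The point holds in this form: SAP 4.9 estimates and tests effects within levels and specifies nothing that measures the difference between them. If levels are compared by significance, identical effects at the design values give one significant half in 42.5% to 45.5% of trials. That rests on a 10-point effect, SD 10, equal halves and balanced arms. Those effect and SD values are stated only for total muscle volume and 6-minute walk distance, 2 of the 15 parameters, and only 4 of the 13 two-level factors are median splits.

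A reader might infer more than the documents support:

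- *That the SAP judges effect modification by significance in one level.* It states no such rule.
- *That these results will select the next study's population.* The SAP speaks only of hypotheses for future study and sets no selection rule.
- *That identical effects look different almost half the time in general.* The table shows otherwise.
- *That the planned tests, up to 27 levels × 15 parameters = 405, with about 40 expected below 0.10 under no effect, show the same fault.* That is multiplicity, which the SAP openly leaves uncontrolled, and 405 is a maximum because levels with fewer than 4 patients are skipped.

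**What to change.** For each two-level factor known at baseline, fit one model with TREATMENT, SUBGROUP, TREATMENT*SUBGROUP and the endpoint's covariates. These factors are the four groupings by weaker-side strength grade (dorsiflexion, plantar flexion, knee extension, and the last two combined), baseline fat fraction, CMT type, CMT1A, braces, baseline CMT-HI, and exercise type among patients with a regular programme. Report the interaction estimate with its 90% CI beside the within-level estimates and 90% CIs. Use the matching term in the recurrent-falls model. State in SAP 4.9 that significance in one level only is not evidence of a differential effect.

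Do not apply this to ADA status or activity level, nor to dose per contractile muscle mass unless that factor is defined for placebo patients. The single-level dorsiflexion subgroup keeps its estimate and CI.

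SAP 4.9 reuses the multiply imputed data, and SAP 4.11.1 names no treatment-by-subgroup term in the imputation, which can pull the interaction towards zero. Either include the term in the imputation model or run the interaction on observed data.

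The cost is SAP wording, one model term per factor and the imputation adjustment; no new data or patients are needed. The downside is imprecision and continued multiplicity: 10 factors × 15 parameters = 150 interaction estimates, of which about 150 × 0.10 = 15 would have 90% CIs excluding no difference if no interactions existed. They should be presented as estimates only.
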